8 ASSESSMENT OF SAFETY

8.1 SPECIFICATION OF SAFETY PARAMETERS

Study participants will be monitored closely based on clinical, laboratory and imaging studies as outlined in study calendar (Table 3). Patients will be educated and encouraged to report any AEs and SAEs promptly. All AEs and SAEs will be graded according to CTCAE v5.0 and recorded in patient's charts and CRFs.

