8.1.1 DEFINITION OF ADVERSE EVENTS (AE)

An adverse event (AE) is defined as any untoward medical occurrence, including an exacerbation of a pre-existing condition, in a patient in a clinical investigation who received a pharmaceutical product. The event does not necessarily have to have a causal relation with this treatment. Grade 1 toxicities and lab abnormalities not deemed clinically significant will not be collected.

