8.3 TIME PERIOD AND FREQUENCY FOR EVENT ASSESSMENT AND FOLLOW-UP

The study participants will be monitored closely throughout the study for occurrence of AE or SAE. The patients will be educated regarding most common AEs and SAEs and will be encouraged to report promptly.

If AEs and SAEs occur, information to be collected includes event description, time of onset, clinician's assessment of severity, relationship to study product, and time of resolution/stabilization of event. All AEs occurring during the study will be documented appropriately, regardless of relationship. All AEs will be followed to adequate resolution.

Any medical condition that is present at the time that the participant is screened will be considered as baseline and not reported as an AE. However, if the study participant's condition deteriorates at any time during the study, it will be recorded as an AE. Unanticipated problems will be recorded in the data collection system throughout the study.

Events will be followed for outcome information until resolution or stabilization is achieved.

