8.4 REPORTING PROCEDURES

8.4.1 ADVERSE EVENT REPORTING

All AEs occurring prior to initiation of Cemiplimab-rwlc therapy do not need to be reported.

All AEs occurring after first administration of Cemiplimab-rwlc therapy and 30 days after last administration of Cemiplimab-rwlc will be considered as on treatment. All AEs will be collected and graded according to CTCAE v5.0, with the exception of Grade 1 laboratory abnormalities which will not be collected. All Grade 2 and above toxicities will be collected and documented by the investigator, but only Grade 3 toxicities deemed possibly, probably or definitely related to the study treatment will be reported on the appropriate CRFs/SAE reporting forms. Only SAEs will be reported to the PI and Regeneron Pharmaceuticals, Inc. All AEs, including those persisting after end of study treatment must be followed up until they have resolved or have been sufficiently characterized or the principal investigator decides to not further pursue them.

Serious and non-serious AEs occurring later than 30 days after last administration of trial drugs will only be reported in case they are considered drug-related or trial (procedure) related.

Deaths (unless they are considered drug-related or trial related) will not be reported as SAE when

they occur later than 30 days after last administration of the trial.

Serious and non-serious AEs occurring after the subjects initiate subsequent treatment will only be collected if deemed related to cemiplimab-rwlc.

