9 CLINICAL MONITORING

Data will be captured in OnCore, Moffitt's electronic Clinical Trials Database. For each participant enrolled, the electronic CRF must be completed by the assigned data manager or other authorized study staff. Any paper forms should be typed or filled out indelible ink and must be legible. Errors should be crossed out but not obliterated, the correction inserted, and the change initialed and dated by the investigator or his/her authorized delegate. This also applies to records for those patients who fail to complete the study. If a patient stops dosing or terminates from the study, the dates and reasons must be noted on the CRF. If a patient terminates from the study because of toxicity, thorough efforts should be made to clearly document the outcome. Regulatory documents and case report forms will be monitored internally according to Moffitt Cancer Center Monitoring Policies. Monitoring will be performed regularly by the MCC Clinical Monitoring Core for accuracy, completeness, and source verification of data entry, validation of appropriate informed consent process, reporting of SAEs, and adherence to the protocol, Good Clinical Practice (GCP) guidelines, and applicable regulatory requirements. The investigator should ensure the accuracy, completeness, legibility, and timeliness of the data reported to the Protocol Monitoring Committee.

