14 DATA HANDLING AND RECORD KEEPING

14.1 DATA COLLECTION AND MANAGEMENT RESPONSIBILITIES

Data collection will be collected by investigators/clinical staff under supervision of the PI. The investigator is responsible for ensuring the accuracy, completeness, legibility, and timeliness of the data reported.

Copies of the electronic CRF (eCRF) will be provided for use as source documents and maintained for recording data for each participant enrolled in the study.

Clinical data (including AEs and concomitant medications) and clinical laboratory data will be entered into Power Chart, a CFR Part 11-compliant data capture system provided by the Cerner. The data system includes password protection and internal quality checks, such as automatic range checks, to identify data that appear inconsistent, incomplete, or inaccurate. Clinical data will be entered directly from the source documents.

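### Section 8.4.1 puts only related Grade 3 toxicities on the CRF where 8.1 puts all AEs there, and the 8.5 halting rule literally omits Grade 4–5 and uses an attribution level that 8.2.2 does not offer

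*Combined protocol and SAP*

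**What the plan says.** **Recording of adverse events**

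- Section 8.1: "All AEs and SAEs will be graded according to CTCAE v5.0 and recorded in" both the chart and the CRF. No grade or relationship limit is given.
- Section 8.3: "All AEs occurring during the study will be documented appropriately, regardless of relationship". The CRF is not named.
- Section 8.4.1, for the period from first dose to 30 days after the last dose: Grade 2 and above are documented by the investigator, but "only Grade 3 toxicities deemed possibly, probably or definitely related to the study treatment will be reported" on the CRFs or SAE forms.
- Section 8.4.2: all SAEs are reported within 24 hours. Deaths and immediately life-threatening events go on the SAE form whatever their cause.
- Grade 1: section 8.1.1 says "Grade 1 toxicities and lab abnormalities not deemed clinically significant will not be collected". Section 8.4.1 collects all AEs "with the exception of Grade 1 laboratory abnormalities which will not be collected". Section 8.1 makes no exception.

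**Data source.** Section 9 captures data in OnCore: "For each participant enrolled, the electronic CRF must be completed by the assigned data manager" or other authorised staff. Section 13.4.1 places the analysis of study data in OnCore as well. Section 10.4.4 tabulates AEs without a filter.

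**Halting rule.** Section 8.5 stops study drug at three Grade 3 AEs that are probably related. Section 8.2.2 gives two causality categories, Related and Not Related. The possibly/probably/definitely wording appears in 8.4.1, without definitions.

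**The concern.** Toxicity, early and late, immune-related and not, is a secondary endpoint (4.2.2). Section 2.1 states that the drug's safety in immunocompromised patients is not known, so describing it is a main product of the trial. Sections 8.1 and 8.4.1 both name the CRF and cannot both be followed. With six sites, some may enter every event and others only related Grade 3 events, and the pooled tables would mix the two.

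Grade 2 matters here because the protocol acts on it. In Appendix 1 Grade 2 colitis and Grade 2 pneumonitis lead to holding the drug, and section 6.1.8 generally stops treatment for Grade 2 uveitis. If non-serious, these are events that 8.4.1 keeps off the CRF.

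The halting rule is the study's one explicit numerical safety stop. As worded, it cannot be read from data recorded on the 8.2.2 scale, and it passes over events worse than those it counts.

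**Working it through.** **The plan's one design figure, for completeness.** Section 10.5 states 83.8% power and actual alpha 0.0986 for n = 27, P0 = 0.15 and a difference of 0.18 (so P1 = 0.33). Success at 7 or more responses of 27 gives P(X ≥ 7 | 0.15) = 0.0986 and P(X ≥ 7 | 0.33) = 0.838. Both reproduce. Neither uses AE data, so the primary test does not depend on this point.

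**Step 1: the two CRF rules side by side** (on-treatment, non-serious events)

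| Event | On CRF under 8.1 | On CRF under 8.4.1 |
|---|---|---|
| Grade 2, any attribution | yes | no |
| Grade 3, related | yes | yes |
| Grade 3, not related | yes | no |
| Grade 4, any attribution | yes | no, read literally |

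Relative to 8.1, the 8.4.1 filter can only remove events. Non-serious Grade 4 events may be few, because immediately life-threatening events are SAEs by 8.1.2 and laboratory data are summarised separately under 10.4.4. The likely losses are mainly Grade 2 and unrelated Grade 3.

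**Step 2: does a loss reach the tables?** Two conditions are needed: a site follows 8.4.1 rather than 8.1, and the tables come from the CRF database. Sections 9 and 13.4.1 point to OnCore for both capture and analysis, so the second condition is the natural reading. The first depends on the site.

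**Step 3: the halting rule against the causality scale**

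| Event | Counted by 8.5 as written |
|---|---|
| Grade 3, probably related | yes |
| Grade 3, definitely related | no, read literally |
| Grade 3, recorded only as Related (8.2.2) | cannot be told |
| Grade 4 or 5, any attribution | no, read literally |

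Section 6.1.8 writes grade ≥ 3 for holding treatment, so the protocol has that form available and does not use it in 8.5.

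**Step 4: could omitting Grades 4–5 change when the rule fires?** The documents give no rate, so the following is assumption only. Let p be the share of patients with a counted event, at most one each, with all 27 treated. Then P(halt) = P(X ≥ 3), X ~ Binomial(27, p).

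- Grade 3 alone at p = 0.05: 0.15. Adding 2 to 5 points for Grades 4–5: 0.29 to 0.52.
- Grade 3 alone at p = 0.10: 0.52. Adding 3 to 5 points: 0.70 to 0.79.

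Section 8.5 counts events as they occur rather than patients at a fixed n, so these values show only that the omission can matter. They do not estimate this trial's chance of a halt.

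**The case against.** The strongest reply is that sections 8.3, 8.6 and 10.4.4 all lean towards full recording, and that 8.4.1 is about reporting. A sensible site would enter everything. That may well happen, but the restricting sentence in 8.4.1 names the CRF and no section says that 8.1 prevails.

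On halting, the reply is that Grade 3 was surely meant as Grade 3 or higher, and that other safeguards exist: 24-hour SAE reporting (8.4.2), possible removal of a patient with a related Grade 4 event (5.4.1), suspension for unacceptable risk (5.5), and monthly committee review (8.6). These are real and lower the risk considerably. A reader might infer that severe events could accumulate unnoticed; the documents do not support that. What stands is narrower: none of these provisions adds Grade 4–5 events to the 8.5 count. Section 8.6 also mentions a data and safety plan that will define stopping criteria, but it ties them to the protocol's own rules.

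Two further inferences are tempting and should not be drawn.

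- *That early and late toxicity use different grade thresholds.* The later-period sentence, "Serious and non-serious AEs occurring later than 30 days after last administration of trial drugs will only be reported" if drug- or procedure-related, restricts by relationship. It names no form and does not say that the grade rule is lifted.
- *That no source for the safety tables is named.* Section 14.1 does say that "Clinical data (including AEs and concomitant medications) and clinical laboratory data will be entered into Power Chart", but 13.4.1 places analysis in OnCore.

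**Conclusion.** The point holds, as two wording defects with practical consequences. First, 8.1 and 8.4.1 conflict on what goes on the CRF. If sites follow 8.4.1, non-serious Grade 2, unrelated non-serious Grade 3 and any non-serious Grade 4 events are missing from the tables for a secondary endpoint. Second, 8.5 as written leaves out Grade 4–5 and definitely related events and relies on an attribution level that 8.2.2 does not supply.

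The size in events or patients cannot be given, because the documents contain no toxicity rates by grade for this population. Only the direction is certain: incomplete tables, and a halt no earlier than it should be. A reader might infer that the trial's toxicity results will be seriously incomplete. That would require knowing which rule sites follow and how common the omitted events are, and the documents show neither. SAEs, deaths and life-threatening events are captured in any case. This should be fixed, but it does not threaten the primary result.

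**What to change.** **(a) One CRF rule.** In 8.4.1, replace the restriction to related Grade 3 toxicities with: *All Grade 2 and above AEs will be entered on the electronic CRF in OnCore regardless of attribution, with relationship to study agent; SAEs are in addition reported per 8.4.2.* Make the Grade 1 exception identical in 8.1, 8.1.1 and 8.4.1. In doing so, say whether the clinical-significance qualifier in 8.1.1 applies to laboratory abnormalities of any grade, since on one reading it would cut into the new rule.

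**(b) One attribution scale and a complete trigger.** Add possibly, probably and definitely as defined levels within Related in 8.2.2, and use them in 8.4.1 and 8.5. Reword the 8.5 trigger to *three Grade 3 or higher AEs judged probably or definitely related*. Replacing probably related by Related alone is not advised: under 8.2.2 a temporal relationship is enough for Related, so with the count kept at three the trigger would widen to events linked by timing only.

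**Cost.** CRF entry at six sites for Grade 2 and above events that 8.4.1 already requires the investigator to document, plus a finer causality field. A halt may come somewhat sooner, because Grade 4–5 and definitely related events now count.

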4.2.2 SECONDARY ENDPOINTS

1. Progression-free survival
2. Overall survival
3. Acute and late immune-related and non-immune-related toxicities

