7.3.5 FOLLOW-UP

To assess for late toxicities, at 6 months and 12 months after EOT patients will return for a physical exam and labs, unless the patient has enrolled in hospice care or is otherwise unwilling/unable to return to clinic.

For this protocol, all patients, including those who discontinue protocol therapy early, will be followed for response until progression and for survival for 2 years from the start of treatment. All patients must also be followed through completion of all protocol therapy. Patients removed from study for unacceptable adverse events will be followed until resolution or stabilization of the adverse event. Follow-up for survival will be performed every 90 days (\pm 2 weeks) from the end of treatment visit.

Research blood collection to be performed at the end of study (2 years after initiation of study treatment).

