8.4.2 SERIOUS ADVERSE EVENT REPORTING

All SAEs will be reported to the PI and Regeneron Pharmaceuticals, Inc. within 24 hours after identification and recorded in OnCore and Regeneron Pharmaceuticals, Inc. by the investigator. All deaths and immediately life-threatening events, whether related or unrelated to the study agent/procedure, will be recorded on the SAE Form and submitted to the PI and Regeneron Pharmaceuticals, Inc. within 24 hours of site awareness. All SAEs will be followed until satisfactory resolution or until the investigator deems the event to be chronic or the adherence to be stable.

The reporting to Regeneron Pharmaceuticals will be done by email, [contact].

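### Sections 8.4.1 and 8.4.2 conflict on unrelated deaths beyond 30 days, and late toxicity is at risk of under-ascertainment because its only two scheduled assessments can be waived with no substitute

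*Combined protocol and SAP*

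**What the plan says.** All references are to the combined protocol and SAP.

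- **Endpoint.** Section 4.2.2 lists as its third secondary endpoint "Acute and late immune-related and non-immune-related toxicities".
- **Late deaths, 8.4.1.** "Deaths (unless they are considered drug-related or trial related) will not be reported as SAE when" more than 30 days have passed since the last dose.
- **Deaths, 8.4.2.** "All deaths and immediately life-threatening events, whether related or unrelated to the study agent/procedure, will be recorded on the SAE Form", to be submitted within 24 hours of the site learning of the event. No time limit is given. Section 16.2 adds further SAE duties on top of 8.4.2 and does not mention the 8.4.1 exception.
- **Late AEs, 8.4.1.** "Serious and non-serious AEs occurring later than 30 days after last administration of trial drugs will only be reported in case they are considered drug-related". Events linked to trial procedures are treated in the same way. Once a patient starts another treatment, only events related to the study drug are collected.
- **AEs in general, 8.3.** "All AEs occurring during the study will be documented appropriately, regardless of relationship".
- **Late visits, 7.3.5.** "To assess for late toxicities, at 6 months and 12 months after EOT patients will return for a physical exam and labs". The section goes on to waive both visits for some patients, in these words: "unless the patient has enrolled in hospice care or is otherwise unwilling/unable to return to clinic". Footnote m of Table 3 repeats this. Footnote k allows the EOT visit to be done by telephone; nothing similar is said for the 6- and 12-month visits.
- **Other contact after EOT.** Section 7.3.5 plans a contact every 90 days from the EOT visit, described for survival only.
- **Length of follow-up.** Section 7.3.5 follows all patients, early discontinuers included, for survival for 2 years from the start of treatment. Section 5.4.2 follows early discontinuers for survival for 1 year from withdrawal.

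**The concern.** There are two separate matters.

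The first is a contradiction in the reporting rules. The study summary gives 6 sites. Two of them could treat the same kind of death in opposite ways and each cite the protocol. The count of deaths reported as SAEs would then depend partly on which section a site reads. Causality review is also touched: 8.2.2 lets the absence of a temporal relationship support a classification of not related, and under 8.4.1 a late death so classed by the treating clinician does not enter SAE reporting.

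The second is ascertainment of a stated endpoint. Patients who have stopped for progression or toxicity may be the ones least able to attend at 6 and 12 months, and the waiver covers exactly that situation. Missing assessments would then plausibly be related to illness. Section 10.4.4 names no denominator for late toxicity, so unassessed patients could be tabulated as if they were free of events. Section 2.1 calls the drug's safety in this population unknown, and with 27 patients one or two missed cases would change the picture.

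**Working it through.** The plan gives no figure on this point. Its one design calculation (27 patients, power 83.8%, one-sided level 0.0986) reproduces with success at 7 or more responses, but it concerns the response rate only.

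**Step 1. The death rules side by side**

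| Death | 8.4.1 | 8.4.2 | Consistent? |
|---|---|---|---|
| Within 30 days of last dose, any cause | exception does not apply | SAE form | yes |
| After 30 days, related | reportable | SAE form | yes |
| After 30 days, judged unrelated | not reported as SAE | SAE form within 24 hours | no |

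Only the last row conflicts. Section 8.3, which documents all AEs during the study whatever their cause, is wider than 8.4.1 as well. Deaths in the last row are not drug toxicity if rightly classified, and those learned of through survival follow-up still enter overall survival.

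**Step 2. Scheduled looks after EOT**

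Inputs: 17 cycles of 21 days (6.1.9); EOT 30 days after the last dose (7.3.4); contacts every 90 days from EOT and visits at 6 and 12 months (7.3.5). Visit windows are ignored.

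- *Full course.* Last dose is day 1 + 16 × 21 = 337, and EOT is 337 + 30 = day 367. Late visits fall at 367 + 183 = day 550 and 367 + 365 = day 732. Two years from the start is 1 + 730 = day 731. Contacts fall on days 457, 547, 637 and 727: **4**.
- *Stopped after dose 2.* Last dose is day 22, and EOT is day 52. Late visits fall at 52 + 183 = day 235 and 52 + 365 = day 417. Under 7.3.5, contacts fall on days 142, 232, 322, 412, 502, 592 and 682: **7**. Under 5.4.2, with withdrawal dated between day 22 and day 52, follow-up ends between 22 + 365 = day 387 and 52 + 365 = day 417, leaving **3 to 4** contacts.

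In each case late toxicity has 2 scheduled looks, or 0 for a patient covered by the waiver. The contacts would bring the first look to 90 days instead of 6 months. For a full-course patient who attends everything, the contacts at 180 and 360 days nearly coincide with the two visits, so the gain is the looks at 90 and 270 days. For a patient who cannot attend, the gain is all four.

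**Step 3. What missed assessments could do (assumptions only)**

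The documents give neither a late-toxicity rate nor a proportion of missed visits. Let *p* be the true rate, *s* the share of patients not assessed and not reported by any other route, and *R* their risk relative to attenders. The rate among attenders is *a* = *p* / [(1 − *s*) + *s* × *R*], and the expected cases seen are 27 × (1 − *s*) × *a*. All 27 are taken to be in follow-up.

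| *p* | True cases | *s* = 10% (*R* = 1; 2) | *s* = 30% (*R* = 1; 2) | *s* = 50% (*R* = 1; 2) |
|---|---|---|---|---|
| 5% | 1.35 | 1.22; 1.10 | 0.94; 0.73 | 0.68; 0.45 |
| 10% | 2.70 | 2.43; 2.21 | 1.89; 1.45 | 1.35; 0.90 |
| 20% | 5.40 | 4.86; 4.42 | 3.78; 2.91 | 2.70; 1.80 |

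At *p* = 10% and *s* = 30%, the chance of seeing any case falls from 94% to 86% (*R* = 1) or 78% (*R* = 2).

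The denominator matters too. At *p* = 10%, *s* = 30% and *R* = 1, dividing by all 27 gives 1.89 / 27 = 7.0%, while dividing by the 18.9 assessed returns 10%. With *R* = 2 the assessed denominator gives 1.45 / 18.9 = 7.7%, still below 10%. The right denominator therefore helps but does not cure illness-related missingness; contacting the missing patients addresses it directly.

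**The case against.** Section 8.4.1 can be read as a specific, time-limited exception to the general rule in 8.4.2. That is a sensible reading, but 8.4.2 says related or unrelated, carries no cross-reference, and is the section that 16.2 builds on. A site could defend either course, so the text has to settle it.

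The protocol also keeps several routes open for late toxicity. Related late AEs stay reportable with no end date, and persisting AEs are followed until resolved, characterised or closed by the principal investigator (8.4.1). Patients removed for unacceptable AEs are followed to resolution or stabilisation (5.4.2, 7.3.5). Those who stop without progression are still followed for response. Unscheduled visits are provided for (7.3.6), and patients are encouraged to telephone (Table 3, footnote j). All of this stands. These routes depend on the patient coming forward or on an event already known, so they reduce the gap in scheduled enquiry without closing it.

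A query to patients in hospice or on later therapy could also collect events that a single-arm study cannot attribute. That is a fair reason to keep the query short and to leave in place the limit to related events after subsequent treatment.

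A reader might infer more than the documents support:

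- *That the death conflict lowers the late-toxicity endpoint.* Related late deaths are reportable under both sections. Only a wrong causality call could carry the conflict into that endpoint.
- *That the sickest patients will skip the visits and the endpoint is under-counted.* The waiver makes this plausible, but no attendance figure is given.
- *That nothing is sought for about 10 months after the early stopper's 12-month visit.* The 731 − 417 = 314 days concern scheduled visits only, and only under 7.3.5. Under 5.4.2 follow-up has ended by then.
- *That AE collection stops at EOT because of the AE row in Table 3.* Column positions are uncertain in the text available here, and footnote m ties the follow-up exam and labs to late AEs.

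**Conclusion.** Both matters call for a revision; neither touches the primary endpoint.

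The contradiction is definite but narrow. It covers deaths judged unrelated more than 30 days after the last dose, and it affects the consistency of SAE death counts and causality review.

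The ascertainment point is a risk, not a demonstrated loss. A stated secondary endpoint has two scheduled assessments after EOT, both waivable, with no remote substitute, while contacts already planned are not used for it. Any under-ascertainment would plausibly be related to illness and would push observed rates down. Its size cannot be derived from the documents, and the table in the working shows only what assumed rates would imply. The contact counts are nominal dates; for early stoppers they depend on which of 5.4.2 and 7.3.5 governs.

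**What to change.** 1. Reconcile 8.3, 8.4.1 and 8.4.2 into one rule for deaths more than 30 days after the last dose, and apply it at all sites.
2. In 7.3.5 and Table 3, add to each existing 90-day survival contact a short query on new or ongoing immune-related AEs and on cause of death. Keep the 8.4.1 limit to related events once a subsequent therapy has begun.
3. Allow telephone or record review when the 6- or 12-month visit cannot be attended, as footnote k already allows by telephone for EOT.
4. In 10.4.4, report late toxicity with the number of patients actually assessed at each time.
5. Reconcile the follow-up length for early discontinuers between 5.4.2 and 7.3.5.

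The cost is wording in a few sections, one short CRF page and a few more minutes at contacts already planned. Reported late-toxicity counts may rise, which should be expected when the tables are read.
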